## 4.6 Methods for Continuous Secondary Outcomes

### 4.6.1.1 *The pain score recorded every 12 hours during the 48 hours period. (Outcome c)*

Linear mixed model with random effects for patients and slopes will be estimated to assess the difference between the groups in overall trend in pain score. The model will include fixed effects for (possibly non-linear polynomial for) time, group dummy and the interaction between the two. Post hoc analyses will be performed to assess between-group differences at each time point as well as within-group changes.

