### **4.6.1.3 Difference in the key pharmacokinetic parameters $T_{max}$ , $C_{max}$ , and $AUC_{0-60}$ after SC and IV administration of morphine bolus doses in steady state morphine infusion in palliative cancer patients (Outcome f)**

Pharmacokinetic parameters will be assessed by drawing IV blood samples for assessment of morphine serum concentrations from a peripheral venous catheter at 0 (baseline), 2, 5, 7, 10, 12, 15, 20, 25, 30, 40, 50, 60, 75, 90, 105, and 120 minutes after a bolus dose when the patient is assumed to be in a pharmacological steady state\*. (\*>24 hours after start of infusion and >2 hours since last bolus dose).

Detailed sampling procedure is described in *SIM-Study Procedure Manual version 1.3, 07.07.22*. The actual time of pharmacokinetic sampling will be used for the determination of all pharmacokinetic parameters. Concentration values will be considered as missing if they cannot be measured due to analytical or clinical issues.  $AUC_{0-60}$  values will not be determined if fewer than three consecutive concentration values are obtained.

In summary statistics and figures plasma concentrations,  $C_{max}$  and area under the curve (AUC) will, if fitted, be adjusted to a normalized 5 mg morphine bolus dose (actual dose in the study: 2.5–20 mg). Morphine concentration at  $t=0$  during steady state before bolus dose will be standardized.

The main absorption and disposition parameters will be calculated for individual concentration time profiles using, if fitted, a noncompartmental model. An independent samples t-test will be used for comparison of  $C_{max}$  and  $AUC_{0-60}$  between SC and IV groups.  $T_{max}$  will be compared using Wilcoxon rank-sum test.

Linear mixed model with random effects for patients and slopes will be estimated to assess the difference between the groups. The model will include fixed effects for time, dose, age, sex, and weight. Post hoc analyses will be performed to assess between-group differences at each time point as well as within-group changes.

$T_{max}$ : The mean (and median) morphine  $T_{max}$  for each mode of administration will be calculated as the average of the protocol-specified time points at which the plasma morphine is highest in each patient.  $T_{max}$  will be reported in the unit of minutes.

$C_{max}$  : Maximum observed concentration, to be reported in the unit of nmol/l (morphine). The geometric mean for each mode of administration will be calculated.

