### 4.6.3 Primary Inferential Analysis

Independent samples t-test for outcomes d) and f). In addition, linear mixed model for outcome c) and f).

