### 4.6.4 Effect Estimates

Mean differences between the groups at each time point with the corresponding 95% CIs.

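### The supplementary PK mixed model lists no route term and gives time no non-linear form, so it cannot validly supply the IV–SC differences at each sampling time that the SAP asks of it

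*SAP*

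**What the plan says.** SAP 4.6.1.3 takes 17 samples per patient: a baseline sample, then samples at "2, 5, 7, 10, 12, 15, 20, 25, 30, 40, 50, 60, 75, 90, 105, and 120 minutes after a bolus dose". Cmax and AUC0-60 are compared by t-test and Tmax by rank-sum test. A further model follows: "Linear mixed model with random effects for patients and slopes will be estimated to assess the difference between the groups". Its terms are given as: "The model will include fixed effects for time, dose, age, sex, and weight". The next sentence states what is wanted from it: "Post hoc analyses will be performed to assess between-group differences at each time point as well as within-group changes".

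SAP 4.6.4 defines the estimate to be reported for the continuous secondary outcomes: "Mean differences between the groups at each time point with the corresponding 95% CIs". SAP 4.6.3 gives the model a supplementary role: "In addition, linear mixed model for outcome c) and f").

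The pain-score model in 4.6.1.1 is specified more fully: "The model will include fixed effects for (possibly non-linear polynomial for) time, group dummy and the interaction between the two". Section 4.6.1.2 extends that specification to bolus counts. Nothing extends it to the PK model.

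**The concern.** The PK model is asked for a result that its listed terms cannot produce. Two elements present in the pain-score model are missing: the group terms (main effect and interaction with time) and any allowance for a curved time course.

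The second omission matters more here than it would for pain. Pain is scored five times over 48 hours. Concentrations are sampled 17 times over 120 minutes after a bolus, and six of the post-bolus samples fall in the first 15 minutes. That grid makes sense only if a rapid early change is expected. If an analyst supplies the missing route terms but keeps time linear, the table of route differences by time point will reflect a straight line rather than the data. It would understate the early IV peak, show a difference before the bolus has acted, and distort the middle and end of the profile.

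**Working it through.** The SAP gives no figure for this model, so there is none to reproduce. The check has two parts.

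**1. The model as listed.** The fixed effects are time, dose, age, sex and weight. With no route term, two patients with the same covariates have the same expected concentration at every time, whatever their route. The route difference is not estimable, and the modelled change over time is the same in both groups. If route were added as a main effect only, the difference would be a single constant at all 17 times.

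**2. Route and route-by-time added, time linear.** With complete, balanced sampling and a random intercept and slope, the fixed-effect estimates equal least squares (confirmed numerically). The fitted route difference is therefore the least-squares line through the true difference at the 17 times.

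Assumed inputs, since the SAP gives no kinetics:
- The IV bolus adds 200 nmol/l, of which 70% declines with a 6 min half-life and 30% with a 120 min half-life.
- SC absorption is complete and first-order, with half-life h = 10 to 20 min.
- The infusion background is equal in both groups and cancels on the raw scale.

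With α = ln2/6, β = ln2/120 and ka = ln2/h:
- IV(t) = 200 × [0.7·exp(−αt) + 0.3·exp(−βt)] for t > 0, and IV(0) = 0
- SC(t) = 200·ka × {0.7·[exp(−αt) − exp(−ka·t)]/(ka − α) + 0.3·[exp(−βt) − exp(−ka·t)]/(ka − β)}
- D(t) = IV(t) − SC(t)

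At 2 min, IV = 200 × (0.7 × 0.794 + 0.3 × 0.989) = 170.4. SC is 23.9 (h = 10) or 12.4 (h = 20), so D is 147 or 158.

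For the line, the mean time is 666/17 = 39.18 min and the sum of squares of time is 23,230.
- h = 10: slope = −12,686/23,230 = −0.546 per min; intercept = 17.04 + 0.546 × 39.18 = 38.4.
- h = 20: slope = −18,294/23,230 = −0.787 per min; intercept = 27.79 + 0.787 × 39.18 = 58.6.

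| Time (min) | True D, h = 10 / 20 | Linear fit, h = 10 / 20 |
|---|---|---|
| 0 | 0 / 0 | 38 / 59 |
| 2 | 147 / 158 | 37 / 57 |
| 30 | −12 / 0 | 22 / 35 |
| 60 | −6 / −7 | 6 / 11 |
| 120 | −3 / −6 | −27 / −36 |

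The sign is wrong at six times when h = 10 (20 to 60 min) and at three when h = 20 (40 to 60 min).

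**Would a polynomial do?** At 2 min a quadratic gives 57–78 and a cubic 70–87, against 147–158.

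**Would a transformation do?** On the log scale, with an assumed background of 60 nmol/l, the 2-min log ratio is 1.01–1.16 and the linear fit gives 0.25–0.43.

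**Other kinetics.** A separate set of 36 scenarios varied the IV distribution half-life (3 or 5 min, or no distribution phase), the SC absorption half-life (5–25 min) and the SC/IV exposure ratio (1–1.5), with a 120 min elimination half-life.
- Linear time: the largest error at any sampling time was 51–113% of the largest true difference (median 68%). At least one sign was wrong in 32 of 36 scenarios on the raw scale and in 29 of 36 on the log scale.
- Quadratic and cubic: the largest errors were 53–85% and 53–72% respectively.

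**The repaired model.** In simulated complete data for 20 patients, route, categorical time and their interaction returned the raw mean differences at all 17 times, with discrepancies below 1e-12.

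**The case against.** The best defence is that the SAP never says time is linear. Random slopes describe the random part and do not fix the form of the fixed effect, and asking for contrasts at each time point is compatible with categorical time. This stands as far as it goes: linear time is an inference from the slopes and from the absence of the wording used in 4.6.1.1. It does not supply the missing route terms, and it leaves unfixed a choice on which the results depend.

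Several stronger readings are tempting, and the document does not support them.

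- **That the PK question is compromised.** The PK research question, hypotheses and outcome f concern Tmax, Cmax and AUC0-60. These are compared directly by rank-sum test and t-test and do not use the model. The model is an addition, in a subgroup of 20.
- **That the time-point contrasts are the model's stated purpose.** The stated purpose is the group difference, and the contrasts are labelled post hoc. Even so, 4.6.4 makes differences at each time point the reported estimate.
- **That the estimates will certainly have the wrong sign.** This depends on kinetics the SAP does not give. Among the 36 scenarios, 4 on the raw scale and 36 − 29 = 7 on the log scale showed no reversal.
- **That the linear fit creates a false reversal late in the profile.** In the worked example the late difference is truly negative. The line exaggerates it, and the wrong signs fall mid-curve.

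A last defence is that assumption checks would catch the misfit. Residual checks (4.6.5) might show it, but the remedies in 4.6.7 are transforming the outcome and robust errors. Robust errors leave the fitted mean shape as it is, and the log scale gave similar errors.

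**Conclusion.** The point holds for the supplementary PK model only. As listed, the model gives no between-route difference at all; this follows from the text and needs no assumption. If route and route-by-time are added and time is read as linear, the time-point differences are badly wrong in size in every scenario tried and wrong in sign in most. In the worked example roughly a quarter to a third of the 2-minute difference is recovered (37/147 = 25%; 57/158 = 36%), and the small late difference of −3 to −6 is reported as −27 to −36. These sizes rest on assumed kinetics, complete sampling and the inferred linear form. Borrowing the polynomial option from 4.6.1.1 would not recover the early peak. The conclusions on Tmax, Cmax and AUC0-60 are untouched, so this is a specification to correct before the PK analysis and not a threat to the main PK result.

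**What to change.** In 4.6.1.3, list the fixed effects as route, nominal sampling time as a categorical variable, and route by time, keeping dose, age, sex and weight. Alternatively, delete the mixed model and rest outcome f on Tmax, Cmax and AUC0-60, with 4.6.3 and 4.6.4 adjusted to match.

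A log scale and a residual correlation that decays with time are optional. If the log scale is chosen, the contrasts become ratios, and 4.6.4, which promises mean differences, must be amended.

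The cost is SAP wording only; no new samples are needed. The downside is more parameters: apart from the intercept and covariates, 1 + 16 + 16 = 33 terms in place of 3 for linear time by route. The planned data are 20 × 17 = 340 concentrations, but these are repeated samples. Each route contrast rests on about 10 patients per arm, assuming the subgroup splits evenly, so the intervals at individual times will be wide.

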### **3.5.1 Pharmacokinetic (PK) subgroup analysis set:**

A subgroup of 20 participants that are enrolled in the study and meet eligibility criteria including the serum measurement specific criteria of Hb>9, and consent to blood sampling are considered for PK analyses.

The PK concentration population includes all study participants who have serum samples after bolus dose available for analysis.. The PK analysis population will be defined as all subjects who have PK data from minimum three concentration measurements.

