$AUC_{0-60}$ : Area under the curve from the time of dosing to 60 minutes will be calculated using a log-linear trapezoidal method. The geometric mean for each group will be reported in the unit of nmol/l/hr.

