### 4.6.5 Assumption Checks and Alternative Analyses

Assumptions for independent sample t-test (normality and homoscedasticity) and linear mixed models (homoscedasticity and normality of residuals) will be assessed by standard methods.

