### 4.6.7 Sensitivity Analyses

If larger deviations from the assumptions of linear mixed model will be identified, transformation of outcome variable or model with robust errors, or both, will be considered.

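### Cmax and AUC0-60 are summarised as geometric means, but the planned t-test names no log scale and no ratio of geometric means is to be reported

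*SAP*

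**What the plan says.** Section 4.6.1.3 (Outcome f) sets out how Cmax and AUC0-60 are summarised and compared.

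- **Summary.** For Cmax: "The geometric mean for each mode of administration will be calculated". For AUC0-60: "The geometric mean for each group will be reported in the unit of nmol/l/hr".
- **Test.** "An independent samples t-test will be used for comparison of" Cmax and AUC0-60 between the routes; Tmax gets a Wilcoxon rank-sum test. Section 4.6.3 repeats the choice: "Independent samples t-test for outcomes d) and f". Neither place names a scale.
- **Effect estimate.** Section 4.6.4 has one sentence for all continuous secondary outcomes: "Mean differences between the groups at each time point with the corresponding 95% CIs".
- **If assumptions fail.** Section 4.6.5 says that the t-test assumptions will be assessed and attaches no action. Section 4.6.7 provides for another model only: "If larger deviations from the assumptions of linear mixed model will be identified, transformation of outcome variable".
- **Size.** Section 3.5.1: "A subgroup of 20 participants that are enrolled in the study".
- **Dose.** Section 4.6.1.3 normalises Cmax and AUC to a 5 mg bolus, with a qualifier, for summary statistics and figures. It does not say whether the test uses the normalised values.

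**The concern.** A geometric mean is the back-transformed mean of the logs. By choosing it, the plan treats Cmax and AUC0-60 as log-scale quantities. A t-test with no scale named, paired with a mean difference, is ordinarily run on the raw values and estimates a difference of arithmetic means. The reader would then see geometric means for each route next to a p-value and interval for something else, with no interval for the contrast that the table invites, which is the ratio. Section 2.4.2 promises 95% intervals for all efficacy estimates, but none is planned for that ratio.

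Two things are at stake: whether the reported result is coherent, and, if the data really are log-normal, some power in a group of 20 patients.

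**Working it through.** **Inputs from the SAP.** Two-sided 5% level (2.4.2); 1:1 allocation (2.2); 20 patients in the PK set (3.5.1). **Assumptions.** 10 per route, since the SAP fixes only the total; log-normal values with equal CV in both routes; CV from 30% to 120%; true geometric mean ratio from 1 to 3. The SAP gives no CV, effect size or power for this outcome. Section 4.9 sizes the trial on the primary outcome alone, so there is no PK figure to reproduce.

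**Step 1: how far apart the two quantities are.** For log-normal data with log-variance σ² = ln(1 + CV²),

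arithmetic mean / geometric mean = exp(σ²/2) = √(1 + CV²).

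- CV 30%: √1.09 = 1.04
- CV 50%: √1.25 = 1.12
- CV 70%: √1.49 = 1.22
- CV 100%: √2 = 1.41

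With equal CVs the factor is the same in both routes. The two ratios then agree, but the arithmetic mean difference is 1.04 to 1.41 times the difference between the geometric means in the table. With unequal CVs even the ratios part. At CV 40% against 100%, equal geometric means give an arithmetic mean ratio of √(2/1.16) = 1.31.

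**Step 2: power.** Simulated rejection rates in %, raw-scale t-test → log-scale t-test, 50,000 trials per cell:

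| CV | ratio 1 | ratio 1.5 | ratio 2 | ratio 2.5 | ratio 3 |
|---|---|---|---|---|---|
| 30% | 4.9 → 5.1 | 81.2 → 83.0 | 99.8 → 99.9 | 100 → 100 | 100 → 100 |
| 50% | 4.6 → 5.0 | 40.1 → 44.3 | 83.1 → 87.4 | 96.7 → 98.4 | 99.4 → 99.8 |
| 70% | 4.1 → 4.8 | 22.6 → 27.4 | 55.3 → 64.5 | 78.0 → 86.7 | 89.8 → 95.7 |
| 100% | 3.7 → 5.0 | 13.1 → 18.1 | 31.0 → 42.1 | 49.1 → 64.5 | 63.2 → 79.7 |

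A further set of 40,000 trials per setting gives, at ratio 2, 44 → 55 for CV 80% and 23 → 34 for CV 120%. At ratio 3 and CV 120% it gives 49 → 69.

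The largest loss is therefore about 2 points at CV 30% (83.0 − 81.2 = 1.8), 4 at CV 50% (87.4 − 83.1 = 4.3), 9 at CV 70% (64.5 − 55.3 = 9.2) and 17 at CV 100% (79.7 − 63.2 = 16.5). With no true difference, the raw test rejects less often than 5%.

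**Step 3: does another section repair it?** Section 4.6.2 offers means or medians, so it names neither a log scale nor a ratio. Section 4.6.5 checks the t-test assumptions without saying what follows. The transformation clause in 4.6.7 is tied to the mixed model and is conditional. By contrast, section 4.4.1 does name a transformation or a non-parametric test as the fallback for the primary outcome. Nothing equivalent covers the t-tests on Cmax and AUC0-60.

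**The case against.** The best reply is that the SAP never says the test is untransformed. The sentence in 4.6.4 speaks of time points, which suits the repeated outcomes; Cmax and AUC0-60 have one value per patient. The effect measure for them may simply be unspecified. That is fair, and it is why the point is put as the plain reading. It does not remove the gap: either the scale is raw and mismatched, or it is open until the data are seen.

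It is also fair that the size rests on assumed CVs, that at CV 30% almost nothing is lost, and that under equal CVs the raw test does not raise false positives.

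Four stronger readings might be inferred, and the material does not support them.

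- *A normality check at 10 per arm could hardly detect the skew.* Under the same log-normal model, a Shapiro-Wilk test at 5% flags at least one arm in about 41%, 65% and 81% of trials at CV 50%, 80% and 120%. The gap is that no action follows a failed check.
- *The 2.5 to 20 mg dose range makes the tested values skewed.* The same section normalises to 5 mg for summaries and figures. Whether the test follows is unstated, so this is a reason to specify it and not evidence of skew.
- *The concentration mixed model must also be fitted on the log scale.* Section 4.6.7 already allows a transformation there, and the calculations above cover only two-sample tests.
- *The trial's conclusion is at risk.* Section 2.4.3 ties the superiority claim to the single primary outcome.

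**Conclusion.** The point holds as a mismatch between the reported summary and the planned inference. As plainly read, the plan tests and estimates arithmetic mean differences while reporting geometric means, plans no ratio, and names no fallback for the t-test.

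The difference between the two kinds of mean follows from log-normality and grows from 4% at CV 30% to 41% at CV 100%. The power loss is conditional on log-normal data, 10 per route, and a CV and ratio that the SAP does not give: negligible to small up to CV 50%, and around 10 points or more from CV 80% at a true ratio of 2. The error is on the conservative side when the CVs are equal. It concerns a pharmacokinetic outcome in 20 patients.

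**What to change.** - In 4.6.1.3 and 4.6.3, state that the t-test is applied to natural-log Cmax and natural-log AUC0-60, and that the test uses the same dose-normalised values as the summaries.
- In 4.6.4, add for these two parameters the IV/SC ratio of geometric means with its 95% CI, obtained by back-transforming the log-scale difference and its limits.
- Keep the Wilcoxon test for Tmax.

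The cost is SAP wording only, with no new data. The change follows the scale that the plan already chose for its summaries. Made before the PK data are analysed, it also removes a choice of scale that could otherwise depend on the results.

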### 4.6.2 Descriptive Statistics

Continuous data will be summarized by means, standard deviations (SDs), and min-max values if data are symmetrically distributed, and median, min-max values and quartiles for skewed data

### 4.6.3 Primary Inferential Analysis

Independent samples t-test for outcomes d) and f). In addition, linear mixed model for outcome c) and f).

### 4.6.4 Effect Estimates

Mean differences between the groups at each time point with the corresponding 95% CIs.

### 4.6.5 Assumption Checks and Alternative Analyses

Assumptions for independent sample t-test (normality and homoscedasticity) and linear mixed models (homoscedasticity and normality of residuals) will be assessed by standard methods.

### 4.6.6 Missing Data

All patients with at least one measurement will be included in the analysis of secondary outcomes (b, c, and d), as the linear mixed model includes all available information, also from dropouts.

### 4.6.7 Sensitivity Analyses

If larger deviations from the assumptions of linear mixed model will be identified, transformation of outcome variable or model with robust errors, or both, will be considered.

### 4.6.8 Subgroup Analyses

None planned.

## 4.7 Methods for Time to Event Secondary Outcomes

### 4.7.1.1 *Time from bolus administration of morphine to clinically significant pain relief (Reduction of 2 on NRS0-10) (Outcome e)*

Time (minutes) from administration of a bolus dose until effect is registered for each bolus dose.

All bolus doses with a minimum of one hour since last bolus dose will be included in the statistical analysis. If a patient is asleep after bolus dose this will count as effect of bolus, but will not be quantified with change in NRS.

Total number of bolus doses and subgroups of bolus doses without effect are summarized as dichotomous variables as part of outcome b) and described in 4.5 *Methods for Dichotomous Secondary Outcomes*

### 4.7.2 Descriptive Statistics

Outcome within treatment groups will be presented by medians and 95% CIs. Robust standard errors will be used to account for possible within-patient correlations due to recurrent events (multiple achieved effects in the observation time).

### 4.7.3 Primary Inferential Analysis

Outcome between the groups will be compared by Cox proportional hazards model with robust standard errors to account for correlated within-patient data due to recurrent events.

### 4.7.4 Effect Estimates

Hazard ratio with corresponding 95% CI will be presented.

### 4.7.5 Assumption Checks and Alternative Analyses

Proportional hazards assumption will be assessed by global test and by examining Schoenfeld's residuals. If this assumption is not met, a model with time-dependent treatment arm variable will be considered.

### 4.7.6 Missing Data

Each patient is supposed to contribute data on all bolus use. If any patients do only contribute data on one or two episodes these episodes will still be included in the analyses, as linear mixed model handles missing data by including all available information from all patients.

